3 STUDY POPULATION

3.1 INCLUSION CRITERIA

In order to be eligible to participate in this study, an individual must meet all of the following criteria:

- 1. Subjects must read, understand and sign the Statement of Informed Consent
- 2. Subjects must be at least 18 years of age
- 3. Subjects must be habitual soft contact lens (CL) wearers, with a daily, weekly, bi- weekly or

- monthly replacement schedule
- 4. Habitual contact lenses must have a suitable fit as determined by the investigator
- 5. Subjects must report a history of dry eye symptoms, for which they have used rewetting drops or Artificial Tears (ATs) in the past 30 days
- 6. Subjects must be willing to discontinue the use of Artificial Tears (ATs) and rewetting drops for the duration of the study
- 7. Subjects must have a score of 12 or higher on the CLDEQ at baseline
- 8. Subjects must have at least 2 of the following signs of dry eye disease:
 - a. High tear osmolarity > 308mOsm/L, or a difference greater than 8 mOsm/L between eyes
 - b. Any corneal staining
 - c. Any bulbar conjunctival staining
 - d. Low TBUT (<10s)
 - e. Schirmer <10mm in either eye
- 9. Subjects must be able to read at least half of the 20/25 (via entrance Snellen visual acuity) or better in each eye in their current contact lens prescription.
- 10. Subjects currently wearing reusable contact lenses must be willing to use Clear Care solution for cleaning and disinfecting throughout the study.

3.2 EXCLUSION CRITERIA

An individual will be ineligible to participate or continue in this study if:

- 1. Currently pregnant or breastfeeding by self-report
- 2. Allergy to lifitegrast ophthalmic solution 5% (Xiidra)
- 3. Habitual extended wear contact lens schedule
- 4. Any active ocular disease that may affect the ocular surface other than dry eye (significant blepharitis, allergic conjunctivitis, lagophthalmos, chalazia, hordeolum etc.)
- 5. Any meibomian gland dysfunction, blepharitis, corneal neovascularization or papillary conjunctivitis that is grade 3 or higher using the Efron Grading Scale.
- 6. Excessive corneal staining, that in the opinion of the investigator, is a contraindication to contact lens use.
- 7. History of ocular surgery
- 8. Any active ocular infection
- 9. Use of any topical ophthalmic medications other than artificial tears or rewetting drops
- 10. Inability to perform necessary visual function assessments
- 11. Punctal plug insertion in the last 3 months, or presence of punctal plugs at the time of the exam.

3.3 SAMPLE SIZE JUSTIFICATION

Assuming normality, we calculated the statistical power for various detectable effect sizes using unpaired t-test in a two-sided hypothesis test with a significance level, 0.05, where the ratio of sample size of 1:1 is assumed between study arms. **Table 1** shows that our sample size will have adequate power to detect listed effect size. For example, we will achieve 84% power to detect a standardized mean difference of 1.12 between two groups of a size of 15 for each, which corresponds to a difference of score change by 3 with standard deviations 3.2 and 2.0 for each group⁵. Up to 40 subjects will be enrolled with the goal of randomizing 30 subjects (15 per arm). This will allow for a 25% screen-failure rate. Note that for each

domain score and the overall score, the power is the same for each effect size since they are standardized, but the mean change corresponding to a given effect size differs.

Table 1

Sample size (N)	Unpaired t-test		
N1 vs. n2	Effect size 1	Power (%)	
15 vs. 15	1	75.3	
	1.12	84.4	
	1.2	87.5	

¹ standardized mean difference of 2 groups

3.4 STRATEGIES FOR RECRUITMENT AND RETENTION

Participants will be recruited from the patients, students, and faculty of the SUNY State College of Optometry without regard to gender, economic status, sexuality, or race. Subjects will also be recruited from outside sources via online recruitment efforts. It will be made clear to those recruited that their participation is completely voluntary, and that failure to participate will have no consequences with respect to their standing within the SUNY community. Participants may withdraw from the study at any time and need not give a reason for doing so.

3.5 ENROLLMENT OF VULNERABLE SUBJECTS

Vulnerable subjects with the exception of employees of the site, and students of the respective university will not be recruited. Staff that is listed on the delegation form are excluded from participation.

3.6 SCREEN FAILURES

Individuals who do not meet the criteria for participation in this trial (screen failure) will not be randomized. There will be no opportunity for rescreening.

4 STUDY INTERVENTION DISCONTINUATION AND PARTICIPANT DISCONTINUATION/WITHDRAWAL

Participants are free to withdraw from participation in the study at any time upon request. An investigator may discontinue or withdraw a participant from the study for the following reasons:

- Cannot comply with instructions in the protocol
- Lost to follow up
- Subject no longer meets eligibility criteria
- Sustain a clinical adverse event (AE), laboratory abnormality, or other medical condition or situation occurs such that continued participation in the study would not be in the best interest of the participant

The following actions must be taken if a participant fails to return to the clinic for a required study visit:

• The site will attempt to contact the participant and reschedule the missed visit and ascertain if the participant wishes to and/or should continue in the study.

- Before a participant is deemed lost to follow-up, the investigator or designee will make every possible effort to contact the subject.
- Should the participant continue to be unreachable, he or she will be considered to have withdrawn from the study with a primary reason of lost to follow-up.

DATA SAFETY AND MONITORING

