2.3 RANDOMIZATION AND MASKING

The randomization schedule will be generated by a biostatistician using simple random sampling. Participants will be randomized within center at the first visit. After all baseline assessments are completed, the delegated unmasked study coordinator will refer to the randomization scheme to assign each subject to one of the two study arms. All study participants who are randomized into the study will comprise the intent-to-treat population. Participants will be randomized into 1 of 2 different treatment arms.

The labeling differences between the lifitegrast and the vehicle will be known to only the unmasked coordinator. The unmasked coordinator will dispense the appropriate treatment to the subject. All drug dispensing and accountability will be done by an unmasked study coordinator so the investigator can remain masked.

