5 STATISTICS

The clinical characteristics of subjects including demographics and lens modality will be first summarized using descriptive statistics in mean \pm SD for continuous variables or % (counts) for categorical variables, with attention to assessing balance in these characteristics by study arms, and with assessment of the distribution of variables, relevant to the choice of statistical tests. For the continuous outcomes, we will conduct the Kolmogorov-Smirnov or the Shapiro-Wilk test to confirm normality of measurements prior to performing statistical analyses. Detection of outliers will be done using histograms, box-plots, normal plots and summary statistics. Where appropriate, logarithmic transformation will be further done.

All analyses will be conducted using the principle of "intent-to-treat" in which every participant is assumed to have received his/her assigned intervention, regardless of adherence. In order to assess for the significant difference between study arms for the primary outcomes of change in total score on the CLDEQ-8 after 8 weeks of treatment or continuous secondary outcomes (change in tear osmolarity), bivariate comparisons will be first conducted using t-tests. Alternatively Wilcoxon nonparametric counterpart will be used for continuous variables that deviate from normality. The forced choice questionnaire will be compared as a percentage of "yes" responses between the two groups by a two-sample test of proportion. These univariate analyses will be followed by multivariable regression methods for an adjustment of all other potential confounding variables such as baseline clinical and demographic characteristics that differ by study arms.

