Alternatively, we will use longitudinal linear models to analyze the difference of changes in total score between study arms from the baseline to the follow-up times across baseline, 2nd, 4th and 8th weeks (i.e., mixed-effects regression models with a random subject effect and GEE with exchangeable and independent correlations). The models will be specified with random intercepts and slopes such that a linear trajectory representing outcome will be compared between groups. Group (arm)-specific (as well as individual-level) intercepts and slopes over the period of follow-up will be included as random effects, while other covariates will be modeled as fixed effects. All models will be adjusted for other clinical or demographic confounders. Residual-based diagnostics will be used to evaluate validity of model assumptions. Two sided p-values <0.05 will be considered to be statistically significant. All statistical procedures were performed using R statistical package (www.R-project.org).

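### Section 4 allows withdrawal from the study with no later CLDEQ-8 and no missing-data rule, so any missing week-8 score makes the first-line test an available-case analysis rather than one of all randomised

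*Combined protocol and SAP*

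**What the plan says.** **Population and principle.** Section 2.3: "All study participants who are randomized into the study will comprise the intent-to-treat population". Section 5 applies intent-to-treat to all analyses, meaning that "every participant is assumed to have received his/her assigned intervention, regardless of adherence".

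**First-line analysis.** For change in CLDEQ-8 total score at week 8, Section 5 says that "bivariate comparisons will be first conducted using t-tests", with a Wilcoxon test if the data are not normal.

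**Second analysis.** Section 5 continues: "Alternatively, we will use longitudinal linear models to analyze the difference of changes in total score between study arms". It covers baseline and weeks 2, 4 and 8, and is set up so that "a linear trajectory representing outcome will be compared between groups". No condition is given for using it, and it is not tied to missing data.

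**Withdrawal.** Participants may leave at any time. Section 4 adds: "An investigator may discontinue or withdraw a participant from the study for the following reasons". One reason is "Cannot comply with instructions in the protocol". Another is an adverse event or other condition that makes continuing not in the participant's best interest. The section heading names both stopping the intervention and leaving the study, but the text does not distinguish them.

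**Missed visits.** Section 4: "The site will attempt to contact the participant and reschedule the missed visit". Someone who stays unreachable is counted as withdrawn.

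**Collection.** The Section 2.4 table has CLDEQ-8 at the four scheduled visits and no early-exit visit.

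**Sample size.** Section 3.3 enrols up to 40 to randomise 30. The margin is for screen failures.

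**The concern.** The participants whom an analysis regardless of adherence is meant to keep are those who stop or misuse the drops. Section 4 allows the same people to be taken out of the study, and nothing then asks for their week-8 score. Section 5 settles which arm a person is counted in. It cannot supply an outcome that was never collected.

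At stake is the comparability of the arms in the primary comparison. If those without a week-8 score differ in symptom change from those with one, and this is not balanced between arms, the estimate shifts. Each loss also comes out of 15 per arm, because the enrolment margin is used before randomisation.

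**Working it through.** **1. The plan's own figure.** Inputs from Section 3.3: difference 3, SDs 3.2 and 2.0, 15 per arm, two-sided 0.05.
- Pooled SD = √((3.2² + 2.0²)/2) = 2.668, so d = 3/2.668 = 1.124.
- Noncentral t, 28 df: power 84.4%, as stated. A Welch test gives 83.9%.
- 40 × 0.75 = 30, so this power assumes a week-8 score from every randomised participant.

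**2. Is a missing score likely?** The documents give no rate. If each participant is lost independently with probability p, the chance that at least one of 30 is missing is 1 − (1 − p)³⁰: 78.5% at p = 5% and 95.8% at p = 10%.

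**3. Random loss costs only power.** The same t-test gives 81.7% at 14/14, 80.1% at 14/13, 78.5% at 13/13 and 74.9% at 12/12.

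**4. Loss related to symptom change.** Assumptions, none from the documents: k = 2 or 3 of 15 are lost on lifitegrast only, and they are the most extreme on a variable correlated r = 0.3 or 0.5 with week-8 change. Section 3.3 does not say which arm has SD 3.2, so both assignments are shown.

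The expected shift in the arm mean is r × SD × S/(15 − k). S is the sum of the k largest expected normal order statistics of 15: 1.736 + 1.248 = 2.984 for k = 2, and adding 0.948 gives 3.932 for k = 3. So S/(15 − k) is 2.984/13 = 0.2295 or 3.932/12 = 0.3277. For example, 0.5 × 3.2 × 0.3277 = 0.52.

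Error and power come from simulation of the Welch test (200,000 trials per setting). With SD 3.2 on lifitegrast and, for estimates and power, a true difference of 3:

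| k | r | Shift | Worst leave: type I error | Worst leave: estimate, power | Best leave: estimate, power |
|---|---|---|---|---|---|
| 2 | 0.3 | 0.22 | 5.7% | 3.22, 85% | 2.78, 74% |
| 2 | 0.5 | 0.37 | 6.9% | 3.37, 89% | 2.63, 70% |
| 3 | 0.3 | 0.31 | 6.1% | 3.31, 85% | 2.69, 68% |
| 3 | 0.5 | 0.52 | 8.4% | 3.52, 90% | 2.48, 63% |

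Allowing for variation between repeat runs, type I error spans about 5.5% to 8.4%. With no loss the results are 5.0%, 3.00 and 84%.

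With the SDs swapped, the shift is 0.14 to 0.33 and type I error about 5.2% to 6.4%. The estimate is 3.1 to 3.3 (power 86% to 89%) if the worst leave and 2.7 to 2.9 (power 73% to 79%) if the best leave.

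**5. Equal loss in both arms.** If the same kind of responder leaves each arm, the shifts partly cancel: r × (3.2 − 2.0) × S/(15 − k) = 0.08 to 0.20. Type I error is about 5.2% to 6.1%. What remains exists only because the SDs differ.

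**6. Reach of a delta analysis.** Shifting each missing score in one arm by 3 points, the clinically important difference in Section 2.1, moves that arm's mean by 3 × 2/15 = 0.4 or 3 × 3/15 = 0.6.

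**The case against.** The plan is not silent. Section 4 requires missed visits to be rescheduled and unreachable participants to be pursued. The Section 5 longitudinal model can use week-2 and week-4 scores from someone without week 8, and it already includes baseline. Follow-up lasts only 8 weeks, withdrawal by the investigator is discretionary, and the investigator is masked. All of this stands and lowers the likely size of the problem. It does not close the gap. The rescheduling duty concerns people who fail to attend, not people already withdrawn. The model is an alternative with no trigger, and it gives a week-8 difference only by assuming a straight line over time.

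Three stronger readings are tempting, and the documents do not support them.
- **That the primary test is a completer analysis that breaks intent-to-treat.** It uses anyone with a week-8 score, adherent or not, and even if week 2 or 4 was missed. With complete scores it is an intent-to-treat analysis. The tension is with the Section 2.3 population, and only once a score is missing.
- **That the result will be biased towards lifitegrast, or that exaggeration and power loss come together.** The direction is unknown. Under a true effect, an exaggerated estimate needs the worst responders to leave lifitegrast and the power loss beyond random loss needs the best to leave. One pattern does not produce both.
- **That the t-test must be replaced as primary.** A mixed model corrects only for loss explained by observed scores. It does not recover scores lost for unobserved reasons.

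**Conclusion.** The point holds in conditional form. The plan promises an analysis of all randomised whatever their adherence, allows people to be withdrawn from the study for non-compliance, and neither collects the primary outcome afterwards nor says what happens when it is absent. If any week-8 score is missing, the first-line test is an available-case analysis.

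The size of any bias is unknown. Under the assumed one-arm losses it is 0.2 to 0.5 points on a true difference of 3, in either direction, and smaller with the SDs swapped or with losses similar in both arms. The top figures need three losses in one arm only and a correlation of 0.5. Confidence is medium. The change should be made because it is cheap and lost scores cannot be recovered later; the documents do not show that the result will be wrong.

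**What to change.** 1. **Main change.** Amend Section 4 to separate stopping the drops from withdrawing from the study. State that anyone who stops drops, or is discontinued by the investigator, is still asked for the remaining scheduled CLDEQ-8 assessments, at least week 8, unless consent is withdrawn. Record lens wear and artificial tear use at that time so the later score can be interpreted. This concerns data collection only and leaves the grounds for stopping treatment as they are.
2. **Analysis.** Analyse all available week-8 scores by assigned arm. Keep the t-test or Wilcoxon test. If any week-8 score is missing, also report the Section 5 mixed model with visit as a category and the week-8 between-arm contrast in change.
3. **Sensitivity and reporting.** Add a delta-adjusted analysis of missing week-8 scores, up to 3 points in either direction and by arm. Report withdrawals and their reasons by arm.

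The cost is protocol and SAP wording, a few extra questionnaires and slightly more analysis. People who withdraw consent will still have missing scores. For them the delta analysis shows only how far the result could move.

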4.1 CONFIDENTIALITY

All information obtained during the course of the study will be regarded as confidential. The Institutional Review Board (IRB), and/or the sponsor may inspect the investigator's records pertaining to the subject as a participant in the clinical study. The results of this study may also be used for medical and/or scientific publications but the subject's identity will not be disclosed. All data to be collected in accordance with HIPAA. All data to be kept as a de-identified data set for subsequent analysis by the investigator.

4.2 HOW WILL CONFIDENTIALITY BE MAINTAINED?

The Principal Investigator and research team will maintain research subject's confidentiality by using coded identifiers on protocol-required information that is reported to the sponsor or leaves the designated research team in any form unless otherwise allowed by the subject through written consent. In order to maintain confidentiality and safety of the human subject, the Principal Investigator and research team will assure that a documented verifiable link exists to identify study subjects throughout the course of the research, including, maintaining the study- specific subject log in a secure location with other regulatory documents at the end of the research study.

To protect the privacy interests of participants, the Clinical Vision Research Center (CVRC) adheres to the following guidelines:

- All study personnel are required to maintain research ethics certification.
- Paper study documents are kept in locked storage in the CVRC and are accessible only by study personnel.
- Electronic study documents are kept in password-protected computer files that are accessible only by study personnel.
- Discussions by study personnel and participants should occur only in the CVRC or in areas where non-study staff or other participants cannot overhear discussions.
- When communicating verbally, by email or by telephone with participants, study staff must ensure they are safeguarding subject confidentiality.
- Only information necessary for the research study is collected from study subjects.

MONITORING

Study initiation, routine and close-out visits are planned and conducted over the lifespan of a study. Study monitoring will be carried out by monitors of the CVRC.

A Site Initiation Visit (SIV) will be conducted prior to site activation to confirm preparedness for protocol execution, satisfactory site facilities, clarify the applicable regulations and requirements of the protocol, carefully review the process of implementing the protocol at the site and conduct any necessary training

prior to the assigned Program Official activating the site for enrollment. The site initiation visit will be conducted as soon as all the necessary approvals have been obtained.

Interim Monitoring Visits (IMVs) will be conducted to confirm subjects' rights are being protected; the study is being conducted according to the protocol and applicable regulations, including GCP; confirm accurate reporting of subject safety data and study endpoints. The first routine monitoring visit will occur as soon as the first subject is recruited or within 2 weeks of the first subject being recruited. The frequency of monitoring will be established at the start of the study.

A Close-Out Visit (COV) will be conducted to ensure that all study data and other study documentation is complete and accurate and that all study records have been reconciled. The COV is completed after data cleansing and data lock.

4.3 RECORD RETENTION

At the end of the study, all study materials (i.e., source, regulatory documents) will be kept on site in a secure area at SUNY College of Optometry. Study materials will only be accessible by research personnel and will be kept for a minimum duration of seven (7) years or longer, if specified in the study contract. Any change to storage location off site will be communicated with the sponsor in advance. Sponsors will be contacted regarding destruction of study material at the end of the prescribed time.

4.4 ANALYSIS

All source data will be collected on paper source documents. Data will be entered into an Excel spreadsheet with double data entry to check for error before locking the data set.

5 STATISTICS

The clinical characteristics of subjects including demographics and lens modality will be first summarized using descriptive statistics in mean \pm SD for continuous variables or % (counts) for categorical variables, with attention to assessing balance in these characteristics by study arms, and with assessment of the distribution of variables, relevant to the choice of statistical tests. For the continuous outcomes, we will conduct the Kolmogorov-Smirnov or the Shapiro-Wilk test to confirm normality of measurements prior to performing statistical analyses. Detection of outliers will be done using histograms, box-plots, normal plots and summary statistics. Where appropriate, logarithmic transformation will be further done.

All analyses will be conducted using the principle of "intent-to-treat" in which every participant is assumed to have received his/her assigned intervention, regardless of adherence. In order to assess for the significant difference between study arms for the primary outcomes of change in total score on the CLDEQ-8 after 8 weeks of treatment or continuous secondary outcomes (change in tear osmolarity), bivariate comparisons will be first conducted using t-tests. Alternatively Wilcoxon nonparametric counterpart will be used for continuous variables that deviate from normality. The forced choice questionnaire will be compared as a percentage of "yes" responses between the two groups by a two-sample test of proportion. These univariate analyses will be followed by multivariable regression methods for an adjustment of all other potential confounding variables such as baseline clinical and demographic characteristics that differ by study arms.

Alternatively, we will use longitudinal linear models to analyze the difference of changes in total score between study arms from the baseline to the follow-up times across baseline, 2nd, 4th and 8th weeks (i.e., mixed-effects regression models with a random subject effect and GEE with exchangeable and independent correlations). The models will be specified with random intercepts and slopes such that a linear trajectory representing outcome will be compared between groups. Group (arm)-specific (as well as individual-level) intercepts and slopes over the period of follow-up will be included as random effects, while other covariates will be modeled as fixed effects. All models will be adjusted for other clinical or demographic confounders. Residual-based diagnostics will be used to evaluate validity of model assumptions. Two sided p-values <0.05 will be considered to be statistically significant. All statistical procedures were performed using R statistical package (www.R-project.org).

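### The normality check that selects t-test or Wilcoxon for the primary outcome is left open between two tests that behave very differently at 15 per arm, with no version, level or unit fixed

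*Combined protocol and SAP*

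**What the plan says.** Section 5 (Statistics) provides for a preliminary check on continuous outcomes: "we will conduct the Kolmogorov-Smirnov or the Shapiro-Wilk test to confirm normality of measurements prior to performing statistical analyses". The default comparison of the arms for the primary outcome is a t-test. The switch is then stated: "Alternatively Wilcoxon nonparametric counterpart will be used for continuous variables that deviate from normality".

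The only significance level in that section is general: "Two sided p-values <0.05 will be considered to be statistically significant". R is named as the software, but no function and no correction to Kolmogorov-Smirnov. The section does not say whether normality is judged in each arm, on the pooled changes or on residuals.

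Section 3.3 plans on the t-test under normality: "we will achieve 84% power to detect a standardized mean difference of 1.12 between two groups of a size of 15 for each", matched to "a difference of score change by 3 with standard deviations 3.2 and 2.0 for each group".

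**The concern.** A preliminary test that selects the primary analysis is part of the primary analysis, so it should be identifiable before the data are seen. Here two tests are joined by an *or*, and they are not interchangeable. Kolmogorov-Smirnov tables assume a fully specified normal distribution. If the mean and SD are estimated from the same sample and no correction is made, the test falls far below its nominal level and has very little power in small samples. Shapiro-Wilk does not have this fault.

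Two things are at stake. An analyst could reach either primary test on the same data and still comply with the plan. And under one permitted reading, the Wilcoxon fallback would rarely operate in the situation it is meant for.

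**Working it through.** **Inputs from the documents.** 15 per arm, two-sided 0.05, difference 3 points, SDs 3.2 and 2.0 (Section 3.3); the two named tests and the switch to Wilcoxon (Section 5).

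**Assumptions, not in the documents.** The normality test is run at 0.05; Wilcoxon is used if either arm rejects; and the non-normal shapes are illustrative. The only distribution the plan mentions is normal.

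**Step 1: reproduce Table 1.** Pooled SD = √((3.2² + 2.0²)/2) = √7.12 = 2.668, and d = 3/2.668 = 1.124. Power comes from the noncentral t with df = 28 and noncentrality d√(15/2):
- d = 1: 75.3% (stated 75.3%)
- d = 1.12: 84.2%, or 84.4% with d unrounded (stated 84.4%)
- d = 1.2: 88.7% (stated 87.5%)

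The planning figures are reproduced to within 1.2 points. They apply to the t-test only.

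**Step 2: critical values.** At n = 15 the 5% critical distance for Kolmogorov-Smirnov is 0.338 from the standard tables. With mean and SD estimated it is 0.219 (Lilliefors, simulated). Using 0.338 where 0.219 is needed is what makes the uncorrected test almost inert.

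**Step 3: rejection rate in one arm of 15, and how often the routes part.** 10,000 simulated samples per shape, so the simulation standard error is at most 0.5 points. The last column compares uncorrected Kolmogorov-Smirnov with Shapiro-Wilk under the either-arm rule.

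| Assumed shape | K-S uncorrected | K-S Lilliefors | Shapiro-Wilk | Different primary test |
|---|---|---|---|---|
| Normal | 0.02% | 4.6% | 5.0% | 10% |
| Normal, whole points, SD 3.2 | 0.06% | 11% | 8% | 14% |
| Normal, whole points, SD 2.0 | 0.15% | 22% | 13% | 24% |
| t(3) | 1.9% | 22% | 27% | 43% |
| Chi-square(4) | 0.5% | 24% | 39% | 61% |
| Exponential | 1.9% | 45% | 67% | 86% |
| Lognormal, σ = 1 | 9.5% | 66% | 82% | 78% |

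The last column can be checked by hand. For exponential data, Shapiro-Wilk rejects in at least one arm with probability 1 − (1 − 0.674)² = 89.4%, and uncorrected Kolmogorov-Smirnov with 1 − (1 − 0.0185)² = 3.7%. The difference is about 86 points. Whole-point normal scores at the pooled SD of 2.668 give about 17%. Milder departures lie between: 27% for t(5) and 38% for a gamma with skew 1.

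**Step 4: effect on the trial's result** (either-arm rule, SD 2.668, 20,000 trials per shape).
- No true difference: type I error is about 4–5% on each fixed route, and the verdicts differ in 0.3–2.5% of trials. Taking whichever route is significant gives at most about 6% (exponential).
- True difference of 3 points: the verdicts differ in about 1% of trials for normal or rounded-normal changes, and in 5–9% for t(3), chi-square(4) and exponential.
- For those three shapes, power is 84–89% by the uncorrected Kolmogorov-Smirnov route and 89–95% by the Shapiro-Wilk route.

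**The case against.** The strongest objection is that the plan never says Kolmogorov-Smirnov would be run uncorrected. A reader might infer that the Wilcoxon fallback is switched off as written, and the documents do not support that. With Lilliefors critical values the test holds its level, and for whole-number normal scores it rejects more often than Shapiro-Wilk. The unit matters too: on 30 pooled values even the uncorrected test rejects 12% of the time for exponential data and 44% for lognormal (σ = 1). This stands, so the near-zero rates are conditional on version and unit. The plan's silence on both is itself part of the gap.

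A reader might also infer that the choice of normality test decides the trial's result or inflates type I error. That is too strong. Under the normality the plan assumes, the two routes usually select the same test. Large disagreement needs skewed or heavy-tailed changes, for which the documents give no evidence. Even then the verdict seldom changes, and neither fixed route exceeds the nominal level materially.

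Finally, the switch depends on deviation from normality, not on a named p-value. Section 5 also refers to assessing distributions when choosing tests, so the formal test may not be the only gate. Log transformation without a trigger, adjustment for characteristics that differ by arm, and alternative longitudinal models leave further freedom. This also stands: removing Kolmogorov-Smirnov alone would not fix the primary analysis.

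**Conclusion.** The point holds in limited form. Section 5 states a data-driven rule for the primary test and leaves open which normality test, version, level and unit drive it. If uncorrected Kolmogorov-Smirnov is used per arm, the Wilcoxon route rarely operates at this sample size; with Shapiro-Wilk it would operate often if changes are skewed or heavy-tailed.

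This is a defect of pre-specification with small numerical consequences, and a low-priority correction. It is worth making because one named option is unsuitable in its uncorrected form and the remedy is nearly free. The sizes rest on the either-arm rule, a 0.05 level for the normality test and the assumed shapes; other choices would move them.

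**What to change.** In Section 5, delete Kolmogorov-Smirnov and stop choosing the primary test by a normality check. Pre-specify one primary analysis: the between-arm comparison of 8-week CLDEQ-8 change, adjusted for baseline CLDEQ-8 score. The baseline score is already collected at Visit 1 (Section 2.4). Report Wilcoxon on the change scores as a named sensitivity analysis, whatever the distribution looks like. Keep residual plots, or Shapiro-Wilk on the residuals, as description only.

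A fixed unadjusted Welch t-test would also remove the ambiguity, but it would give about the same result as the uncorrected Kolmogorov-Smirnov route and so adds little.

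The cost is a wording change and one extra sensitivity line, with no added participants, visits or measurements. The downside is possibly slightly lower power than Wilcoxon if changes prove strongly skewed.
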